### **3.2 Allocation to Treatment Groups and Blinding (if applicable)**

There will be no randomization or blinding for this study. All 24 subjects will receive the “SPM Active” intervention. Baseline measurements will be taken prior to intervention so that each subject may serve as his/her own control.

### **3.3 Study Duration, Enrollment and Number of Subjects**

Each subject’s participation will last up to 4 weeks +/- 2-4 days, with no additional time involved in this study outside normal pre- and post-operative care. The entire study is expected to last 6-9 months. This includes an enrollment period of 3-4 months and data analysis.

### **3.4 Target Population**

#### Inclusion Criteria:

- Male and female subjects with age 50-65 years and obese (i.e. BMI 30-40) who are euglycemic and pre-diabetic (i.e. fasting glucose 70-125 mg/dL or HbA1c of 5.7-6.4%).
- Only post-menopausal females will be recruited in the female cohort to reduce the confounding inflammatory effects of estrogen with supplementation.

#### Exclusion Criteria:

- Those with fasting glucose values > 126 mg/dL or known type 2 diabetes
- Females who are pre-menopausal, pregnant, planning to become pregnant, breastfeeding or lactating
- Subjects consuming n-3 PUFA supplements in the last 3 months prior to enrollment, high consumption of fatty fish (>2 servings per week), and subjects with active autoimmune disease, liver disease, coagulopathy, hypothyroidism, known allergy to fish or shellfish, inability to give informed consent, or taking anticoagulants (e.g. warfarin and direct acting anticoagulants), those taking estrogen or testosterone, and anyone taking daily aspirin, NSAIDs, or active asthma medications.
- Subjects receiving immunomodulatory or immunosuppressant therapy (corticosteroids or monoclonal antibodies) in the 4 weeks prior to study enrollment, and subjects with known active malignancy or undergoing treatment for malignancy will be excluded.

Demographics: No exclusions will be made based on race, gender, or ethnicity. Since all female subjects will be post-menopausal, this study will not include female subjects who are pregnant or become pregnant. This is not because we expect risk to mother or fetus in pregnancy but rather because of the hormonal effects of high estrogen in pre-menopausal women on the lipidomic profile that we are studying. Moreover, the inflammatory effects of estrogen will confound the lipidomic profile measured from the subjects. For this reason, the female cohort will include only post-menopausal women.

## **4 STUDY PROCEDURES**

### **4.1 Screening/Baseline Visit procedures**

Insulin (ng/dL), glucose (mg/dL), BMI (kg/m^2), weight (lbs), height (ft), disease status, and medications will be abstracted from medical charts. These metabolic measurements will be compared pre- and post-

supplementation for aim2a, and used to investigate their association with SPM concentrations for aim2b.

12-hour fasting blood and serum will be drawn for each subject by a licensed phlebotomist at the UNC Family Medicine Lab and under the direction of [name] at baseline. Each blood sample will be the size of 10 10mL plasma and serum tubes (9 plasma tubes + 1 serum tube). PBMCs will be isolated from each blood sample. SPM concentration will be compared in the plasma, serum and PBMCs obtained for each patient, in accordance with aim 1a. For aim 1b, we will plate 15 wells of B cells (isolated from the PBMCs) for activations with 200,000 B cells per well ( $3 \times 10^6$  total). We are assuming 1 mL blood yields approximately  $1 \times 10^6$  PBMCs. We also assume  $0.5 \times 10^6$  PBMCs per well with 5% B cells. Since, on average, 7-8 mL of blood is collected per 10mL tube, we will collect 10 tubes to ensure we have at least 60 mL blood for the  $60 \times 10^6$  PBMCs needed to collect  $3 \times 10^6$  B cells for activations. Therefore, a total of 10 tubes or ~100 ml of blood will be drawn.

In addition to blood collection, each subject will have his/her height (ft), body weight (lbs), blood pressure (mmHg), and pulse taken (bpm).

#### **4.2 Intervention/Treatment procedures**

All subjects will receive the dietary supplement “SPM Active”, provided free of cost by Metagenics. Subjects will be responsible for taking 4 capsules per day (2 at breakfast and 2 at dinner) for a total of 4 weeks.

#### **4.3 Follow- up procedures**

There is no scheduled follow up procedure apart from that detailed in the study design. The patients will follow up in a routine manner as designated by their physician at UNC Family Medicine.

#### **4.4 Unscheduled visits**

The study coordinator may relay health concerns to [name] that will necessitate an in-person visit.

#### **4.5 Concomitant Medication documentation**

All prescription or OTC drugs taken by study subjects will be examined by [name] and his team prior to enrollment in the study. No previous adverse events have been observed in previous studies (such as the human clinical trial done by Dalli et al.) with “SPM Active,” though we will continuously monitor subject health status via phone contact at the end of week 1 and week 3.

#### **4.6 Subject Completion/ Withdrawal procedures**

Subjects will be compensated \$250 cash for their participation and completion of the study (\$100 at baseline visit + \$150 at week 4 visit upon completion). No prorated compensation will be applied for this pilot study. This amount of compensation is not deemed coercive; the incentive is meant to compensate subjects for their time in the study which include two study visits, two phone visits, and two blood draws.

This is a voluntary research study. Refusal to participate or withdrawal of participation and/or consent can occur at any time, for any reason. Subjects may be withdrawn if: (1) they experience intolerable adverse reactions or allergic reaction to study supplement or (2) are not at least 90% compliant with taking study supplement during the 4 weeks active phase. In the event of withdrawal, all personal health information (PHI), electronic or hard copy, will be immediately purged and permanently destroyed. Withdrawal or

refusal will not influence ability, timing, or quality of clinical care, type of clinical care administered, standing with UNCHC system, or ability to participate in future research studies. The investigators also have the right to stop participation at any time. This could be because participants have chosen to stop supplementation, or have failed to follow instructions or because the entire study has been stopped.

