## **7 STUDY INTERVENTION**

The “SPM Active” supplement will be shipped all at once from Metagenics at room temperature to the UNC Family Medicine clinic with expiration that covers the full duration of the intervention. Study participants will be instructed to keep the supplement at room temperature. Subjects who have consented to the study will receive the exact number of tables required for the study. They will be instructed to consume 4 capsules per day (2 capsules with breakfast and 2 with dinner) of “SPM Active” for 4 weeks. Each capsule contains 145 mg of SPMs for a total daily dose of 580 mg. There are 3 metabolites of the SPM family in the capsule, which are 17-HDHA (40mg) + 14-HDHA (80mg) + 18-HEPE (25mg). All three metabolites feed into pathways shown to improve insulin resistance and all three metabolites are decreased in obese subjects. The rationale for the dosing and time of intervention is based on the recommendations by the manufacturer. Appropriate dosing will be monitored with the follow-up phone calls at weeks 2 and 3. Participants who have chosen to stop supplementation, or have failed to follow supplement instructions will be withdrawn from the trial.

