## **9 SAFETY MANAGEMENT**

Safety standards will be overseen by Co-Investigator, [name], DO and his designated study coordinator. Subjects will be screened for adverse events during two follow-up phone calls at Weeks 1 and 3 of intervention, as well during last study visit, Week 4. Subjects will be given the study coordinator’s phone number to report any Adverse Events or Serious Adverse Events. All reported Adverse Events (AEs) will be given to the co-investigator, [name], each week of the study.

Should a Serious Adverse Event (SAE) occur, [name], co-investigator, will be immediately notified. The subject will be instructed to stop study drug, and seek immediate medical attention. SAEs include but are not limited to bleeding, chest pain/pressure, shortness of breath, weakness, altered mental status, vision changes or extreme pain.

A log of all AEs will be maintained throughout the study and will be assigned to each patient. Note that this study will not require a Data Safety Monitoring Board (DSMB) due to its small sample size and the low risk of study drug. However, [name], co-Investigator, will review weekly the adverse event reporting log for all subjects. Any clinically significant AEs will be follow-up by [name] and the study coordinator to ensure resolution. Patients will be further evaluated by [name] or other health care professional for ongoing AEs.

Though highly unlikely, if 50% or more of total study participants report intolerable adverse reactions from taking the supplement, we will stop the study.

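### Section 4.6 appears to put $150 of the $250 payment at risk for a subject who admits missed doses, although self-report is the plan's only adherence measure; the same holds, more weakly, for intolerable reactions

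*Combined protocol and SAP*

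**What the plan says.** **Payment.** Section 4.6 gives $250 "cash for their participation and completion of the study": $100 at the baseline visit and $150 "at week 4 visit upon completion". It then states that "No prorated compensation will be applied for this pilot study". The same paragraph gives the purpose: "the incentive is meant to compensate subjects for their time in the study", listing two visits, two phone contacts and two blood draws.

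**Withdrawal.** Section 4.6 permits, but does not require, withdrawal if "they experience intolerable adverse reactions or allergic reaction to study supplement", or if compliance is under 90%. Section 7 is mandatory: those who choose to stop, or who "have failed to follow supplement instructions will be withdrawn from the trial". Section 4.6 also says that a withdrawn subject's personal health information is purged immediately.

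**Where the facts come from.** Under Section 2.2 (Aim 2a) the coordinator asks subjects how far they complied, and Section 7 monitors dosing by phone. Section 7 dispenses the exact number of units but describes no count or return of unused capsules. For adverse events, Section 9 says "Subjects will be screened for adverse events during two follow-up phone calls at Weeks 1 and 3 of intervention". It adds screening at the week 4 visit and a phone number for subjects to report events themselves.

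**Stopping rule.** The Synopsis (Safety Evaluations) and Section 9 stop the study if half or more of participants report intolerable reactions.

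**The concern.** Each provision is ordinary by itself. Together they attach money to the content of a self-report. The subject is the only source on missed doses, an admission below the threshold can lead to withdrawal, and withdrawal appears to end entitlement to the larger payment.

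Three things could suffer:

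- **The primary comparison.** Under-dosed subjects who say nothing stay in the pre/post analysis as compliant. That would pull the SPM change towards zero and leave no trustworthy adherence variable to explain a null result. The plan relies on 9 subjects per sex.
- **Tolerability and stopping.** The study-level rule counts reports, so an intolerable reaction that is not reported does not count.
- **The stated purpose of the payment.** A subject withdrawn after the week 3 call has given one visit, one blood draw and both phone contacts, yet appears to receive none of the $150.

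**Working it through.** **1. Payment (Section 4.6).** The plan's total reproduces: $100 + $150 = $250. Share that depends on completion: 150/250 = 60%.

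**2. Admission that crosses the 90% line.** The inputs are 4 capsules a day (Section 4.2), 4 weeks with a margin of up to 4 days (Synopsis; Section 3.1) and 90% compliance (Section 4.6). Capsules due = 4 × days. Capsules needed = 0.9 × due, rounded up. The failing number of misses = due − needed + 1.

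| Days | Due | Needed | Misses that fail |
|---|---|---|---|
| 24 | 96 | 87 | 10 |
| 26 | 104 | 94 | 11 |
| 28 | 112 | 101 | 12 |
| 30 | 120 | 108 | 13 |
| 32 | 128 | 116 | 13 |

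At 28 days, 12 misses leave 100/112 = 89.3%. That is 12/4 = 3 days of dosing. Fewer misses do not breach the 90% criterion.

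**3. Who supplies the information.**

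- *Adherence:* only the subject, by answering the coordinator. No diary, capsule count or biomarker is named as a check. Post-treatment SPM levels are an endpoint and are not designated as an adherence measure.
- *Adverse events:* mainly the subject, by phone, but also at the week 4 visit. Self-report by phone is therefore not the only route.

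**4. What each report can cost.**

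- *Compliance under 90%, admitted before the week 4 payment:* withdrawal is permitted by Section 4.6, and failure to follow instructions makes it mandatory in Section 7. The $150 is at risk.
- *Intolerable or allergic reaction, reported before week 4:* withdrawal is discretionary, so the $150 is at risk only if the investigator withdraws the subject or the subject stops.
- *Milder event:* no cost.
- *Silence:* no cost.

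**5. Stopping rule.** The threshold is 0.5 × 24 = 12 reports. To show how a rule that counts reports responds to silence, let p be the true proportion with intolerable reactions and r the share of those who report. Both are assumed; the documents give neither. The chance of reaching the threshold is P(X ≥ 12) with X binomial(24, p × r).

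| p | r = 1 | r = 0.9 | r = 0.8 | r = 0.6 |
|---|---|---|---|---|
| 0.5 | 0.581 | 0.385 | 0.213 | 0.031 |
| 0.6 | 0.886 | 0.726 | 0.502 | 0.113 |
| 0.7 | 0.988 | 0.935 | 0.788 | 0.277 |

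This shows sensitivity only. The plan expects adverse events to be unlikely, and at low true rates 12 reports would not be reached with or without concealment.

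**6. Payments.** If all 24 are paid in full: 24 × $250 = $6,000. If, for example, 6 subjects stop early but attend week 4: 6 × $150 = $900, within that total. The 6 is borrowed from 24 − 18 in Section 6.4 and is not a limit.

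**The case against.** The strongest reply is that forfeiture is nowhere stated. The clause can be read as a fixed payment for each visit, with no splitting between visits, and it names neither adherence nor adverse events. Terms on withdrawal would normally be in the consent form, which was not part of the review copy. The incentive also operates only if subjects know of the 90% rule and connect it with payment. All of this stands: the loss is an inference from the completion condition, the bar on proration and the withdrawal rules.

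The adverse-event half is open to further challenge. The mandatory wording in Section 7 covers stopping and not following instructions; it does not cover reporting a reaction. Week 4 screening also comes when dosing is ending. This stands too, and the adverse-event half is accordingly the lesser part of the point.

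A reader might go further and infer that adherence reports will be inflated and reactions under-reported. The documents show a reason to misreport and give no rate, so they do not support that as a finding. Nor do they show that paying for attendance would by itself obtain a second sample: Section 7 removes those who stop, no blood draw after withdrawal is described, and Section 4.6 purges their health information. Finally, $900 is neither a ceiling nor a budgeted sum. The increase from 18 to 24 allows for loss to follow-up, which Section 4.7 applies to subjects who cannot be reached by phone, and no payment budget is given.

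The reply does not remove the adherence incentive. No section preserves the $150 for a subject withdrawn after an honest answer, and no second source of adherence data is described.

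**Conclusion.** The point holds as a low-cost improvement to the payment wording, not as a demonstrated bias. As written, 60% of the payment appears to depend on not being withdrawn, and an admission of 12 or more missed capsules at 28 days (10 to 13 across 24 to 32 days) can lead to withdrawal when nothing but the subject's word would reveal it. For intolerable or allergic reactions the same reasoning applies with less force.

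The conclusion assumes that a withdrawn subject does not count as a completer for payment, that the consent form does not say otherwise, and that subjects understand the link. Any resulting bias would tend to overstate adherence, dilute the SPM change and under-count reports for the stopping rule. Its size cannot be computed from the documents.

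**What to change.** 1. In Section 4.6, replace the completion condition and the no-proration sentence with payment of the $150 for attending the week 4 visit and blood draw, regardless of reported adherence, early stopping or adverse events. Align the consent form with this.
2. Have the coordinator say at consent and on each call that missed doses and side effects do not affect payment.
3. Reconcile the permissive withdrawal wording in Section 4.6 with the mandatory wording in Section 7. State whether a withdrawn subject may attend week 4, and how the purge of personal health information applies to that subject's data and samples. Without this step the change removes the reporting penalty but does not secure a second sample.

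The cost is protocol and consent wording, plus payment to some subjects who stopped early ($900 in the example of 6). Total payments cannot exceed $6,000 for 24 subjects. The incentive to return at week 4 is kept, and payment then matches the stated purpose of compensating time.

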### **5 STUDY EVALUATIONS AND MEASUREMENTS**

Samples taken from pre- and post-intervention visits will be immediately transferred to [name] ([name] Lab) for immediate processing. Tubes will be labelled with a de-identified research code and will not include any PHI. We will measure SPMs in 100µl of plasma and serum and  $2 \times 10^6$  PBMCs. PBMCs will be isolated with established protocols in our lab. The rationale for PBMCs vs. plasma and serum is to compare biomarkers for SPM uptake. We will also measure other lipid metabolites including thromboxanes, leukotrienes, prostaglandins, epoxy fatty acids, eoxins, mono-, di-, and tri-hydroxy fatty acids, and hepoxilins. Blinded samples will be shipped to our collaborator [name] (pay-for-service, see support letter) for two-dimensional reverse phase HPLC tandem mass spectrometry. Blood samples from baseline and post-intervention will be used to measure fasting glucose (mg/dL), fasting lipid panel (total cholesterol in mg/dL, LDL in mg/dL, HDL in mg/dL, triglyceride levels in mg/dL) and fasting insulin (ng/mL) through McClendon labs.

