## **10 DATA COLLECTION AND MANAGMENT**

Personal identifiers and medical history will be collected following patient recruitment and informed consent.

Data from this study will be kept in electronic and hard copy forms with the respective security measures. Electronic data will be kept on an encrypted desktop computer protected by multiple passwords in a lab, located on a hall protected by card access in Michael Hooker Research Center, Chapel Hill, NC. De-identified data will be stored on REDCap for use by research team personnel only. Data management will be performed by the PI and the study coordinators. All data acquisition will meet HIPPA and confidentiality standards. Electronic data will be stored for a minimum of five years in the case that this data needs to be verified. When deemed appropriate, all files will be purged and permanently deleted from research computers. Hard copy data will be shredded. Human biological samples (serum/plasma) will be stored for a minimum of five years in the case that these samples are needed for duplication of or verification of study results. Please see Part C for further details. These samples will be stored in locked freezers in locked research laboratories in secure facilities that require card access. When all analysis of human biological samples is completed, all samples will be disposed of according to university and environmental health guidelines. Data that links dummy identifiers to any personal identifying information will be shredded and disposed of, or, in the case of electronic data, will be permanently deleted. Limited clinical data (glucose, insulin, lipid panel) may be part of subjects' secure electronic medical record in Epic.

Note that the biological samples and data collected from subjects who are lost to follow-up will be handled in this way as well.

The PIs will be responsible for monitoring and reviewing subject data, lab results, study progress, subject safety and confidentiality, and the accuracy and security of the emerging data. They will also be responsible for running the assays and entering all data into redcap for statistical analysis.

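### Section 4.6 destroys all PHI at once on any withdrawal, with no exception for an open adverse event that Section 9 requires the study to follow to resolution

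*Combined protocol and SAP*

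**What the plan says.** Section 4.6 lets a subject withdraw at any time for any reason. It also lets the investigators withdraw a subject, and the first ground listed is that "they experience intolerable adverse reactions or allergic reaction to study supplement". The data rule follows directly: "In the event of withdrawal, all personal health information (PHI), electronic or hard copy, will be immediately purged and permanently destroyed". It is not limited by reason for withdrawal.

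Section 7 is firmer about who is withdrawn: "Participants who have chosen to stop supplementation, or have failed to follow supplement instructions will be withdrawn from the trial".

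Section 9 sets the safety duties. "A log of all AEs will be maintained throughout the study and will be assigned to each patient". Clinically significant AEs are to be followed up by the co-investigator "and the study coordinator to ensure resolution", and patients with ongoing AEs are to be evaluated further. Neither duty excludes withdrawn subjects.

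Section 5 separates the research code from PHI: "Tubes will be labelled with a de-identified research code and will not include any PHI". Section 10 keeps electronic data for at least five years, and applies the same handling to subjects lost to follow-up. It does not mention withdrawn subjects.

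**The concern.** A subject who leaves because of a reaction is the one most likely to have an event still open on the day of leaving. That is also the day on which Section 4.6 has the study destroy the means of reaching that person and of tying a later outcome to the log entry. A subject who completes the course with an open event faces no such purge, and data from one who cannot be reached by phone are kept under Section 10. The plan is therefore least able to follow the group for which follow-up matters most.

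What is at stake is the completeness of the safety record: an AE may stay in the log with no outcome, or with no patient to whom it can be assigned.

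**Working it through.** The plan states no figure on this point, so the check is a comparison of the rules.

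1. **Does the purge reach a withdrawal for a reaction?** Yes. Section 4.6 lists a reaction as a ground for withdrawal, and the data rule that follows applies to withdrawal without distinction.

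2. **Can staff avoid the conflict by delaying withdrawal?** Only sometimes.
   - Where the investigators decide, Section 4.6 says the subject may be withdrawn, and Section 5.2 has the clinician evaluate whether to do so. They could wait until the event resolves.
   - After a serious AE, Section 9 tells the subject to stop the supplement. That instruction is not in itself a withdrawal.
   - A subject who withdraws by choice leaves no such room. Nor, on the wording of Section 7, does a subject who chooses to stop the supplement because of a reaction. Section 4.6 treats that last case as an investigator's right, so the two sections also differ in force.

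3. **What does the purge remove?** The plan expands PHI as personal health information but does not list its contents. Section 5 says that coded tubes carry none, which implies that identifying details are PHI. I therefore assume that contact details, and the key linking code to person, fall under the purge. Section 10 shows that such a key exists: "Data that links dummy identifiers to any personal identifying information will be shredded and disposed of". Read with the sentence before it, that disposal comes after sample analysis is complete. Section 4.6 brings it forward to the moment of withdrawal.

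4. **What does Section 9 need?** Follow-up by the study to resolution needs a way to reach the patient. A patient-assigned log needs a way to attach the outcome to the right entry. Both depend on what step 3 removes.

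5. **Is there an exception elsewhere?** I looked in the synopsis and in Sections 4.7, 5.2, 7, 9 and 10. None exempts safety records from the purge. Section 10 extends ordinary retention only to subjects lost to follow-up, whom Section 4.7 defines as those the coordinators cannot contact by phone.

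Result: for a subject withdrawn with a clinically significant AE still open, Section 4.6 and Section 9 cannot both be carried out as written.

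**The case against.** The strongest reply is that little of practical value is lost. The rule covers PHI only, so coded samples, the de-identified REDCap data and an AE log kept under the research code would survive. Subjects are recruited at clinic visits and return to their clinic physician. Section 4.6 says withdrawal does not affect care, Section 9 allows another health care professional to evaluate ongoing AEs, and some clinical data may sit in the clinic's electronic record. The consent pages were not available for this review, nor was the Part C to which Section 10 refers; either may already deal with retention after withdrawal.

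All of this stands, and it limits the harm. It does not remove the conflict. The plan does not say that the log is coded, and it names no route by which an outcome known to the clinic would reach the study's log after the purge.

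A reader might also infer more than the documents support:

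- **That the 50% stopping rule would be undercounted.** Section 9 stops the study "if 50% or more of total study participants report intolerable adverse reactions from taking the supplement, we will stop the study". This counts reports over all participants. A report already made is not undone by a later withdrawal, and counting it needs no identifier.
- **That the allowance from 18 to 24 subjects sizes the problem.** Those 24 - 18 = 6 extra subjects are for loss to follow-up, a separate group whose data are retained. They are not a forecast of withdrawals for AEs.
- **That safety oversight rests on the weekly log review alone.** Section 10 also makes the PIs responsible for monitoring subject safety, and Section 9 adds AE screening at weeks 1, 3 and 4 and immediate notification of serious AEs.

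**Conclusion.** The concern holds in a narrow form. As written, Section 4.6 prevents the study from meeting its own Section 9 duty for one kind of subject: a person withdrawn while a clinically significant AE is open. What is lost is the study's ability to follow that event itself and to record its outcome against the right entry. It does not follow that the AE count is lost or that the patient goes without care.

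The number affected cannot be derived from the plan, which gives no rate of reactions or of withdrawals for AEs. It is probably small: Section 4.5 reports no adverse events in earlier studies of the supplement, and Section 9 regards widespread intolerance as highly unlikely. The primary SPM comparison does not change.

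The conclusion rests on two assumptions: that PHI includes contact and linking details, and that no document outside the visible text already provides an exemption. The change is worth making because two stated rules collide on a safety matter and a short amendment settles it.

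**What to change.** 1. **Section 4.6, with cross-references from Sections 7 and 9.** Add an exception to the purge. For any subject withdrawn with an AE, the AE log entry and the contact and linking details are kept until the event resolves. The identifiers are then destroyed, and the coded AE record is kept for the Section 10 retention period (at least five years).
2. **Same place.** If the subject refuses further contact, destroy the identifiers and keep only the coded entry.
3. **Section 9.** State that the AE log is kept under the research code, so that an entry does not itself count as PHI to be purged.

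If the consent form or Part C already provides this, a citation in Section 4.6 is enough.

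The cost is wording in three sections; it adds no visits or assays beyond the follow-up that Section 9 already requires. The downside is one of privacy: identifiers of these subjects are held somewhat longer than now promised, and a coded entry stays on file even for someone who refuses contact. The consent wording must say so.
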